### **Day 0**

- ✓ Diet Habit Survey;
- ✓ TPB questionnaire;
- ✓ Baseline Cognition test;
- ✓ HbA1c results: participants should have a recent (less than 1 month from study start) HbA1c test or head to local lab for testing.

Diet Habit Survey will be answered by a link sent to participants through RedCap-UBC.

Cognition test will be sent as a link to be answered in a quiet room. Tests will last approximately 10 minutes.

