### **Day 1**

- ✓ Blood sample collection
- ✓ Insert CGM 1

Blood drops will be collected by participants after having fasted overnight (8-10 h) and refrain from taking any medications on the morning to measure the primary outcome of HbA1c and associated secondary outcomes measures of fasting plasma glucose, insulin, blood lipid profile and inflammation. Envelope will be then sent to research team by mail.

CGM instructions will also be sent and a Zoom meeting can be scheduled to help participants with insertion of device.

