### **Blood samples**

Blood will be collected at 2 timepoints, one at baseline and the other at the end of the trial. For the primary outcome of HbA1c, participants will be asked for results from a recent HbA1c test in 2 time points: a) less than a month from study start and b) less than one week from study end. If they a recent exam is not available, participants will be asked to go to their nearest local lab for a recent HbA1c blood test. They will receive a requisition by e-mail and will not need to pay or have a doctor’s referral for the exam. Participants with high levels of A1c (>8.5%) during screening will be notified via email and not eligible for the study. For secondary

outcomes, a dried blood spot device will be used for sampling. Dried blood spot is a form of collection where patients place blood drops on a filter card after a finger prick with a lancet. Once dry, blood spot cards are extremely stable for shipment and storage, and the dried blood format offers excellent correlation with serum tests. The same laboratory providing the blood spot will analyze primary outcome of HbA1c and associated secondary outcomes measures of fasting plasma glucose, insulin, blood lipid profile (triglycerides, total, HDL, and LDL cholesterol) and inflammation (high-sensitivity C-reactive protein [CRP]).

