## **SAMPLE SIZE CONSIDERATIONS**

We used a previous breakfast intervention in T2D along with our recently published one-day egg-based low-carbohydrate (LC) breakfast trial to calculate the sample size for this RCT. Rabinovitz et al  compared a “big breakfast” containing higher fat and protein providing 33% total daily energy to a small breakfast providing 12.5% daily energy over 3 months in a similar sample of participants with T2D using a similar parallel-group design. They reported an absolute reduction in HbA1c% of 0.46% in the big breakfast group. This is similar to the magnitude of change observed in a recent study by Nichols et al  who reported an average HbA1c reduction of 0.45% in response to metformin, the standard prescribed medication for people newly diagnosed with T2D. For this reason, it is reasonable to use the study published by Rabinovitz et al to estimate a clinically relevant effect size for our sample size calculation. A medium effect size (Cohen’s  $d = 0.46$ ) was calculated from the Rabinovitz study. In agreement, for our recent one-day study examining an egg-based LC breakfast (3), the effect size (Cohen’s  $d$ ) for improvements in CGM-derived glucose control variables (including AUC, iAUC, glycemic variability, and mean) ranged from  $d = 0.48-1.2$ .

Taking a conservative approach, we used an effect size of  $d = 0.4$  in the sample size calculation. The total sample size necessary to detect a between-within interaction using a repeated measures ANOVA with an effect size of  $d = 0.4$  (which corresponds to an ANOVA effect size  $f = 0.2$ ) with 90% power and 5% type 1 error with a conservative correlation among repeated measures of  $r = 0.5$  is 68 ( $n = 34$  per group, calculated using G\*Power v3.1.9.2). To account for a 20% dropout rate (2), we aimed to recruit a sample size of  $n = 41$  per group. These calculations were documented in the original grant application (Feb 2019), trial protocol (Dec 6, 2019), and SAP (Nov 17, 2021).

Adjustment as of 16th January 2022:

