**Secondary outcome measures:** To supplement the primary outcome of A1c, continuous glucose monitors (CGMs) will be worn by participants during the first and last 14 days of the intervention (i.e., both timepoints of CGM will be collected while participants are consuming their allocated breakfast). Changes in CGM variables (fasting glucose, mean glucose, maximum glucose, minimum glucose, 24-h area under the curve, incremental area under the curve, MAGE, SD, time below 3.9 mmol/L, time above 10mmol/L , time in range (3.9-10 mmol/l); 2-hour post-meal: incremental area under the curve, mean glucose, maximum glucose and SD will be calculated for each 14 day period. CGM data will be analyzed using a linear mixed model that will include fixed effects for timepoint (First 14 days vs Last 14 days), group (LC vs. CTL), their interaction, and stratified allocation factors (sex) and random effects for participants. In this analyses the main effect of group will be most important to identify an overall effect of the intervention on glycemic control variables.

Continuous secondary outcomes will be analyzed similarly to the primary outcome using a constrained baseline longitudinal data analysis linear mixed model (with all relevant follow-up timepoints included as a fixed factor in the model). Secondary outcomes include:

1. Changes in self-reported satiety and fullness assessed with a 100 mm visual analogue scale (VAS) on satiety and fullness at baseline, midpoint and 12 weeks, which were based on those validated by Flint et al. (1).
2. Changes in self-reported dietary intake (total kilocalories, grams of carbohydrates and percent of total calories, grams of protein and percent of total calories and grams of fat

and percent of total calories, egg consumption) assessed via self-report (3-day dietary records) at baseline, midpoint and 12 weeks.

3. Changes in self-reported body weight and body mass index from baseline to 12 weeks.
4. Changes in blood markers (fasting insulin, high-sensitivity C-reactive protein, triglycerides, total cholesterol, HDL, LDL and VLDL) from baseline to 12 weeks.
5. Changes in carotenoid levels (lutein and zeaxanthin) from baseline to 12 weeks.
6. Changes in cognitive function from baseline to midpoint and 12 weeks.

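### The CGM mixed model omits the pre-diet HbA1c the trial already collects, and so probably gives up some precision for metrics close to average glucose

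*SAP*

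**What the plan says.** The SAP (Analysis Objectives, Outcomes, and Statistical Methods, secondary outcomes) gives CGM its own linear mixed model. The terms are timepoint (first versus last 14 days), "group (LC vs. CTL), their interaction, and stratified allocation factors (sex) and random effects for participants". It states that "both timepoints of CGM will be collected while participants are consuming their allocated breakfast". It then names the result of most interest: "In this analyses the main effect of group will be most important to identify an overall effect of the intervention".

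HbA1c and the other continuous secondary outcomes are analysed differently, by a constrained longitudinal model in which a baseline value is one of the repeated measures.

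A pre-diet HbA1c is part of the schedule. At Day 0 the Protocol says "participants should have a recent (less than 1 month from study start) HbA1c test", with a local-laboratory test as the alternative. Its Blood samples section repeats that "participants will be asked for results from a recent HbA1c test in 2 time points". The Protocol's Background describes HbA1c as a marker of average glycaemia over the preceding 90 to 120 days.

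This value is not a covariate in the CGM model. The SAP's Sensitivity Analysis section adds site, adherence and egg intake, but not baseline HbA1c. The Protocol's Statistical Analysis section names only age and sex.

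**The concern.** The CGM group effect is a comparison between people. Differences in glycaemia that existed before the diet stay in its error term, and the model's only baseline covariate, sex, is unlikely to remove much of them. The other continuous outcomes gain precision from their own baseline; CGM has no equivalent, although a related pre-diet measure is on file.

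The SAP presents CGM as supplementing the primary outcome. If pre-diet HbA1c correlates with a CGM metric, the confidence interval for that metric will be wider than it needs to be. The documents give no power calculation for CGM. The only CGM effect sizes are from the group's one-day study: "improvements in CGM-derived glucose control variables (including AUC, iAUC, glycemic variability, and mean) ranged from" 0.48 to 1.2. Added precision matters most near the low end of that range.

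There is also a point of wording. The overall group effect most naturally means the average over both windows, but the contrast is not written out. In a model with an interaction, the coefficient labelled group depends on how timepoint is coded.

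**Working it through.** **The plan's own figure.** The SAP's sample size is for HbA1c: f = 0.2, two timepoints, correlation 0.5, two-sided 5%. The noncentrality is f² × N × 2/(1 − 0.5) = 0.04 × 68 × 4 = 10.88, with 1 and 66 degrees of freedom. Power is 0.9015, so the stated 68 (34 per group) reproduces. There is no corresponding CGM figure, so 34 per arm is borrowed below.

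**Inputs.**
- From the documents: two on-diet CGM windows, 34 per arm, CGM effect sizes 0.48 to 1.2, planning effect 0.4, and baseline HbA1c present for 78 of 92 randomised by January 2022 (14/92 = 15.2% missing).
- Assumed: correlation r between HbA1c and the CGM metric (the same in both windows, or read as the average over them), and between-window correlation ρ = 0.7.

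**Variance of the group effect.** With window SD 1, the two-window mean has variance (1 + ρ)/2 = 0.85. A covariate correlated r with each window explains R² = r²/0.85 of it. The SE ratio is √(1 − R²). If a share m of baseline values is replaced by the overall mean, R² becomes R² × (1 − m).

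| r | R² | SE ratio | SE cut, complete | SE cut, 10% mean-filled | SE cut, 15.2% mean-filled |
|---|---|---|---|---|---|
| 0.3 | 0.106 | 0.946 | 5.4% | 4.9% | 4.6% |
| 0.5 | 0.294 | 0.840 | 16.0% | 14.3% | 13.4% |
| 0.7 | 0.576 | 0.651 | 34.9% | 30.6% | 28.5% |

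**Cost of the extra coefficient.** Multiplying the variance by about 1 + 1/(68 − 5) = 1.016 changes the complete-data cuts to 4.7%, 15.3% and 34.4%. At r = 0 the SE rises by 0.8%. Break-even is at r of about 0.12.

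**Sensitivity to ρ.** At r = 0.5 with complete values, the cut is 18.4% for ρ = 0.5 and 14.2% for ρ = 0.9.

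**Simulation.** With 8,000 trials per setting, 34 per arm, sex in the model, a true effect of 0.4 and 15.2% of baselines missing at random, mean estimates were 0.398 to 0.404 whether unadjusted, adjusted or mean-filled. The SE cuts were 4.9%, 16.4% and 34.4% complete, and 3.8%, 13.6% and 28.0% mean-filled. At r = 0 the SE rose by 0.6% to 0.7%.

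**Power** (noncentral t, two-sided 5%, 34 per arm, ρ = 0.7, effect in window SDs, complete baseline values):

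| Effect | Unadjusted | r = 0.3 | r = 0.5 | r = 0.7 |
|---|---|---|---|---|
| 0.4 | 42% | 46% | 55% | 77% |
| 0.48 | 56% | 61% | 71% | 90% |
| 0.8 | 94% | 96% | 99% | >99% |
| 1.2 | >99% | >99% | >99% | >99% |

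With 15.2% mean-filled, power at 0.48 is 60%, 69% and 84% for the three values of r. The standardiser behind the 0.48 to 1.2 range is not stated and the data are from one day, so those effects may not carry over.

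**The case against.** The strongest reply is that this is a preference about a supplementary outcome. The model is valid, nothing in the documents requires HbA1c adjustment, and no power is claimed for CGM. All of that stands, and it limits the point to an optional improvement.

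The size can also be challenged. The HbA1c may be up to a month old at Day 0, while the last window runs from Day 70 to Day 84, so a weaker later correlation is plausible. With correlations of 0.5 then 0.3, the average is 0.4, R² = 0.16/0.85 = 0.188 and the SE cut is 9.9%. For 0.7 then 0.5 it is 24%, and for 0.3 then 0.1 it is 2.4%. This arithmetic is right. It amounts to reading r as the average over the two windows, and the results stay within the span already shown. The HbA1c entry limit of below 8.5% and results from differing laboratories could also lower r, so the 35% end should not be read as expected.

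The gain is least certain where the Protocol puts weight, on the post-breakfast spike. That stands too. With equal correlations, the timepoint-by-group interaction gains little or nothing.

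Lastly, the SAP rules out imputation, and it links the missing baselines to dropout after randomisation, whereas the simulation assumed missingness at random. The imputation objection is met by confining the exception to the covariate. The missingness mechanism remains an assumption.

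**Conclusion.** The omission is real and its consequence is limited to precision. There is no bias and no error in the planned model. For mean glucose, 24-hour AUC and time above 10 mmol/L a gain is likely; time in range probably belongs with them. For iAUC, MAGE, SD, the 2-hour post-meal set, minimum glucose and time below 3.9 mmol/L the gain is unknown and may be small.

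At a moderate correlation of 0.5 the SE falls by roughly 13% to 16%, depending on missing baselines, and power at an effect of 0.48 rises from 56% to between 69% and 71%. The loss if HbA1c is uninformative is under 1% of the SE. These figures depend on assumed correlations, on both windows being observed for 34 per arm, and on the one-day effect sizes carrying over. Confidence in the size is therefore moderate, although the direction is clear for metrics near average glucose.

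**What to change.** By a dated SAP amendment before unblinding, add baseline HbA1c as a fixed covariate in the CGM models, and specify three things.

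1. **Source.** Use the recent or local-laboratory result for every participant, dated before the first study breakfast. The Protocol is not consistent here. Day 1 describes the blood spots as taken "to measure the primary outcome of HbA1c and associated secondary outcomes measures", and Blood samples adds that "The same laboratory providing the blood spot will analyze primary outcome of HbA1c", alongside the recent-result route. The two sources should not be mixed.
2. **Missing baseline values.** Fill them with the overall mean, ignoring arm, so that nobody with CGM data is dropped. State this as a covariate-only exception to the no-imputation rule.
3. **Contrast.** Add one clause defining the group effect as the LC minus CTL difference averaged equally over the two 14-day windows.

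The SAP dates study completion to June 2022. If unblinding has already occurred, keep the planned model as the main CGM analysis and report the adjusted one as a labelled sensitivity analysis.

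The cost is one amendment, one named covariate source and one missing-value convention, with no new data. Missing values may be fewer among CGM wearers than the 14 of 92 overall, because the SAP ties the shortfall to dropout.

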## **BACKGROUND AND AIM:**

From December 2019 to June 2022, we completed the study titled “Impact of a low-carbohydrate versus low-fat breakfast on blood glucose control in type 2 diabetes” at two study sites, at the University of Wollongong (UOW) and the University of British Columbia (UBC). The aim of the trial was to determine whether a low-carbohydrate high-fat (LC) breakfast (with breakfast meals focused around eggs as a main ingredient), compared to a standard low-fat control (CTL) breakfast (designed to have no/minimal eggs) would improve blood glucose control in individuals with type 2 diabetes (T2D). The primary outcome measure was change in Hemoglobin A1C (HbA1c) following the 12-week dietary intervention. Secondary outcomes included changes in satiety and daily caloric intake, body weight, body mass index, glucose control assessed by continuous glucose monitoring, insulin, C-reactive protein, blood lipid profile, carotenoid levels, and cognitive function. It was hypothesized that consuming a LC breakfast would improve blood glucose control, increase satiety, and improve body composition and cognitive function in people with T2D.

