## **ANALYSIS OBJECTIVES, OUTCOMES, AND STATISTICAL METHODS**

All data were collected longitudinally. Statistical analysis will be performed blinded to participant allocation after the last participant has completed the trial.

**Primary endpoint:** The prespecified primary outcome for this trial will be a comparison of the change in HbA1c (in the standard percentage units) from baseline to 12 weeks between the dietary intervention groups.

The analysis of the primary outcome is based on a superiority approach (i.e., we expect that the LC intervention will be superior in leading to decreased HbA1c compared to the CTL intervention). Data will be analyzed by constrained longitudinal data analysis (cLDA) via a linear mixed model with fixed effects for timepoint (baseline and week 12), the interaction between timepoint and dietary intervention group, and stratified allocation factors (sex) as well as random effects for participants to account for the correlation of repeated measures within participants.

The cLDA approach constrains the baseline means to be equal between the treatment groups, which is a reasonable assumption in the context of a randomized controlled trial. If a participant does not have any HbA1c recordings in the end of the trial, only the baseline value of that participant will be included in the model and no post-intervention value for that participant will be included. No missing data will be imputed as per contemporary guidelines. Model specification will be assessed visually using normal probability plots and residuals vs. fitted values plots. Models will be run using log-transformed outcome variables when departure from model assumptions is observed.

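### For satiety and food records, the SAP forces equal arm means at a 'baseline' that the protocol schedules in week 1, very likely on the diet

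*SAP*

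**What the plan says.** The SAP (Analysis Objectives, Outcomes, and Statistical Methods) describes the primary model thus: "The cLDA approach constrains the baseline means to be equal between the treatment groups". It calls this reasonable in a randomised trial. Under Secondary outcome measures it carries the same model over: "Continuous secondary outcomes will be analyzed similarly to the primary outcome using a constrained baseline longitudinal data analysis linear mixed model". The entry for the visual analogue scale (VAS) reads "on satiety and fullness at baseline, midpoint and 12 weeks", and the entry for dietary intake reads "via self-report (3-day dietary records) at baseline, midpoint and 12 weeks".

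The protocol has different timepoints. Research Method, the participant instructions and Dietary assessment place the food records, and Research Method and Dietary assessment the VAS, at weeks 1, 6 and 12. Day 7 is the first visit that lists either. The Day 0 list has the Diet Habit Survey, the TPB questionnaire, the cognition test and HbA1c, but no VAS and no 3-day record.

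For CGM the SAP notes that "both timepoints of CGM will be collected while participants are consuming their allocated breakfast". It uses a model with a group main effect and no equal-means constraint.

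**The concern.** Randomisation makes the arms equal in expectation before treatment begins. It gives no such assurance a week into two different diets. If the SAP's baseline for these outcomes is the protocol's week-1 visit, the model sets to zero an arm difference that may be real, and it uses that false equality to adjust the later visits.

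Satiety and daily caloric intake make up Objective 2 of the protocol, and this model provides their between-arm test. Carbohydrate, fat and egg intake show whether the two arms actually ate different diets, and they are fitted the same way. The SAP also treats similar data in two ways: CGM, first collected in the same fortnight, is left unconstrained because it is on-diet.

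**Working it through.** **1. Is week 1 just a loose name for baseline?** It does not appear so. The protocol puts the cognition test at weeks 0, 6 and 12 in Research Method, and at days 0, 42 and 84 in the instructions, so it separates week 0 from week 1. It provides for exactly three food records, and the SAP names three timepoints. A pre-diet record would be a fourth.

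**2. Is Day 7 on-diet?** Very likely, on three grounds.
- The SAP describes the primary outcome as "change in Hemoglobin A1C (HbA1c) following the 12-week dietary intervention", and the study ends on Day 84. 84/7 = 12 weeks, whereas a diet starting after Day 7 would last at most (84 − 7)/7 = 11 weeks.
- The first CGM sensor is worn from Day 1 to Day 14, and the SAP calls that period on the allocated breakfast.
- The protocol section on potential problems says that the food logs at weeks 1, 6 and 12 document consumption of the study diets.

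**3. Do the arms differ by week 1?**
- *Carbohydrate and fat at breakfast* (menu ranges in Dietary assessment). With 400 kcal in both arms, carbohydrate differs by at least 400 × (0.45 − 0.10)/4 = 35 g and fat by at least 400 × (0.65 − 0.35)/9 = 13.3 g. In the least favourable calorie mix the gaps are 400 × 0.45/4 − 500 × 0.10/4 = 32.5 g and 400 × 0.65/9 − 500 × 0.35/9 = 9.4 g. These become daily differences given adherence and no compensation at other meals.
- *Eggs.* Probably: the LC arm is described as "with breakfast meals focused around eggs as a main ingredient" and the CTL arm as "designed to have no/minimal eggs".
- *Satiety and total calories.* Possible, but not established, because breakfasts are matched on calories and protein. The protocol does report lower hunger in its own one-day study.

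**4. Size of the bias.** Let D_t be the observed arm difference at week t, with true value δ_t, and let rho be the within-person correlation. With complete data and equal correlations, the constrained estimate at week t is D_t − rho × D_1. Its expectation is δ_t − rho × δ_1, so the bias is −rho × δ_1.

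The documents give no rho, SD or effect size for these outcomes, so the values below are assumptions. The 34 per arm comes from the sample-size section. It reproduces: noncentrality 0.2² × 68 × 2/(1 − 0.5) = 10.88 gives power 0.9015.

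Simulation: 34 per arm, three complete visits, random-intercept REML, sex in the model, 1,500 trials per cell, true effect 0.5 SD at weeks 6 and 12. The share of the week-12 effect recovered by the constrained model is shown below, with the formula's value in brackets.

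| Week-1 effect | rho 0.3 | rho 0.5 | rho 0.7 |
|---|---|---|---|
| Same as later | 70% (70) | 49% (50) | 28% (30) |
| Half | 84% (85) | 75% (75) | 65% (65) |
| None | 102% (100) | 99% (100) | 99% (100) |
| Half, opposite sign | 116% (115) | 125% (125) | 134% (135) |

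The Monte Carlo standard error is at most 0.012. The unconstrained model recovers 99–102% throughout. When the effect is the same at all visits, p<0.05 occurs in 32/21/13% of constrained analyses at rho 0.3/0.5/0.7, and in 54/53/54% of unconstrained ones.

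Larger constant effects do worse, because the misfit inflates the fitted rho (800 trials per cell). At 1 SD, recovery is 67/45/26%. At 2 SD it is 54/32/18%, with fitted rho 0.46/0.67/0.83.

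**5. An early effect that fades.** With 0.5 SD at week 1 and zero at weeks 6 and 12, the constrained week-12 estimate averages −0.15/−0.25/−0.36 SD, against −0.15/−0.25/−0.35 by formula. It reaches p<0.05 in 9/22/54% of trials, versus about 5% unconstrained. A separate run at 0.4 SD showed the same pattern: −0.12/−0.21/−0.29 SD, with 7.5/17/38% of trials significant.

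**The case against.** The strongest reply is that the bias is conditional. Neither document defines baseline for these outcomes. The SAP was written with knowledge of the trial's conduct, and its authors deliberately separated on-diet CGM from the rest, which fits knowledge of a pre-diet VAS and food record as well as it fits an oversight. The protocol's day lists are also incomplete: starting weight is on neither the Day 0 nor the Day 1 list, and Day 70 is missing from the Study Timeline. This stands as a reason to check dates before changing anything. It does not remove the conflict between the documents, and the count of three food records weighs against an unlisted fourth.

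Second, the bias is surest where it matters least. No hypothesis concerns carbohydrate, fat or egg intake, and daily intake differs as the menus do only if other meals do not compensate. That is fair, and it is why no bias in grams is claimed. It limits confidence for satiety and calories to moderate.

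Third, the percentages rest on assumed correlations, effects and complete data, while the SAP reports complete HbA1c data for only 62 of 92 randomised. They illustrate the formula and are not forecasts for this trial.

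**Conclusion.** The concern holds. The conflict between the SAP's baseline label and the protocol's week-1 schedule is plain, and Day 7 is very likely on-diet; confidence in this is high. If no pre-diet measurement exists, the equal-means constraint is unjustified for the satiety VAS and the food records. The later contrasts are biased by about −rho times the week-1 arm difference. They shrink if the early effect has the same sign, are inflated if it is opposite, and are unbiased if there is none. An early effect that fades shows up reversed.

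Distortion is expected for carbohydrate and fat, given adherence and no full compensation at other meals, and is probable for egg intake. For satiety and calories confidence in distortion is moderate. The primary HbA1c analysis is not affected. This should be corrected, but it does not threaten the trial's main result.

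**What to change.** 1. Confirm from the collection dates when the first VAS and food record were taken relative to the first allocated breakfast. Include the Godin activity score, an exploratory outcome with the same mismatch.
2. If they were on-diet, label that visit week 1 and drop the constraint for these outcomes. Use the model already specified for CGM: timepoint, group, their interaction, sex and a random participant effect. Report LC − CTL differences at weeks 1, 6 and 12, and their average. Label any within-group change (SAP, Sensitivity analysis) as change from week 1; that model has no equal-means constraint, so only the label changes.
3. If a true pre-diet measurement exists, state its timing in the SAP and keep the constrained model.

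The cost is a date check, some SAP wording and one model statement; no new data are needed. If there is truly no week-1 effect, the unconstrained model loses precision. For a 0.5 SD effect at week 12, the chance of p<0.05 is 56/52/53% against 59/66/80% constrained, at rho 0.3/0.5/0.7. That loss matters most for satiety and calories, so the model change should depend on the date check.
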